1.2. Statistical Hypotheses for Trial Objectives

No formal statistical hypothesis testing is planned for this study. This is because the primary purpose of the study is to provide descriptive information regarding safety and immunogenicity of the 2 vaccination regimens within cohorts of healthy and HIV-infected subjects.

1.3. Trial Design

This is a randomized, observer-blind, placebo-controlled, parallel-group, multicenter, 2-part, Phase 2 study to evaluate the safety, tolerability and immunogenicity of different vaccination regimens using Ad26.ZEBOV at a dose of 5×10^{10} viral particles (vp) and MVA-BN-Filo at a dose of 1×10^8 infectious units (Inf.U, nominal titer), administered intramuscularly. The first regimen to be evaluated is a first vaccination with MVA-BN-Filo followed by a second vaccination with Ad26.ZEBOV 14 days later. The second regimen to be evaluated is a first vaccination with Ad26.ZEBOV followed by a second vaccination with MVA-BN-Filo 28 days

later. Both regimens are being evaluated in healthy and HIV-infected adults, aged 18 to 70 years, inclusive at screening. An overview of the study vaccination schedules is provided in [Table 1](#).

A total of 575 subjects were planned to be enrolled, with approximately 300 healthy subjects and 275 HIV-infected subjects. Eligible subjects were those who had never received a candidate Ebola vaccine and had no prior exposure to EBOV (including travel to epidemic Ebola areas less than 1 month prior to screening) or a diagnosis of EBOV disease. See the CTP¹ for further details.

Table 1: Study Vaccination Schedules for Parts 1 and 2

Part 1: United States of America (USA), N=75			
MVA-BN-Filo on Day 1, Ad26.ZEBOV on Day 15			
Active		Placebo	
Healthy Adult	HIV+ Adult	Healthy Adult	HIV+ Adult
40	20	10	5
Part 2: Africa, N=500			
Group 1: Ad26.ZEBOV on Day 1, MVA-BN-Filo on Day 29			
Active		Placebo	
Healthy Adult	HIV+ Adult	Healthy Adult	HIV+ Adult
160	160	40	40
Group 2: MVA-BN-Filo on Day 1, Ad26.ZEBOV on Day 15			
Active		Placebo	
Healthy Adult	HIV+ Adult	Healthy Adult	HIV+ Adult
40	40	10	10

1.4. Sample Size Justification

An overall sample size of 575 subjects was expected and had to include 460 subjects who had to receive active 2-dose vaccination and 115 subjects who had to receive placebo. The data obtained in these subjects will substantially contribute to the overall safety database of the Ebola program. See Section 11.1 of the CTP¹ for details on the sample size justification.

1.5. Randomization and Blinding

Both Parts 1 and 2 of the study have completed randomization. Central randomization was implemented in this study. The randomization was used to minimize bias in the assignment of subjects to vaccination schedules (groups), to increase the likelihood that known and unknown subject attributes (eg, demographic and baseline characteristics) are evenly balanced across groups, and to enhance the validity of possible comparisons across groups. In addition, randomization was used to minimize bias in the assignment of subjects to study vaccine (active vaccine versus placebo). The randomization within each group was balanced by using randomly permuted blocks. There was stratification by age group (subjects ≥ 18 to ≤ 50 years versus subjects > 50 years).

For Part 1, subjects were randomized in a 4:1 ratio to either receive MVA-BN-Filo or placebo on Day 1 followed by a second vaccination with Ad26.ZEBOV or placebo 14 days later. Randomization was done separately for healthy subjects (N=50) and HIV-infected subjects (N=25).

For Part 2, subjects were randomly enrolled in 1 of 2 groups at study entry to either receive Ad26.ZEBOV,MVA-BN-Filo at day 1 and day 29 or MVA-BN-Filo, Ad26.ZEBOV at day 1 and day 15 in a 4:1 ratio (ie, Group 1 versus Group 2). Within each group, subjects were randomized in a 4:1 ratio to receive active vaccine versus placebo. Randomization was done separately for healthy subjects (N=250) and HIV-infected subjects (N=250). The start of randomization of HIV-infected subjects in Part 2 was contingent upon acceptable safety data from HIV-infected subjects from Part 1.

For each part, study-site personnel (except for those with primary responsibility for study vaccine preparation and dispensation, and not involved in any other study-related procedure), the sponsor (except for specifically designated sponsor personnel who are independent of the study) and subjects will remain blinded to the study vaccine allocation until the last subject in that part has completed at least the 6-month post second vaccination visit or discontinued earlier and the database has been locked for that part.

Data that may potentially unblind the study vaccine assignment (ie, study vaccine preparation/accountability data, immunogenicity data or other specific laboratory data) will be handled with special care to ensure that the integrity of the data is maintained and the potential for bias is minimized. This can include making special provisions, such as segregating the data in question from view by the investigators, clinical team, or others as appropriate until the time of database lock and unblinding. The pharmacy and preparation of study vaccines was monitored by an independent study vaccine monitor.

2. GENERAL ANALYSIS DEFINITIONS

The type I error rate (α) is set to 0.05 and corresponding 2-sided 95% confidence intervals (CIs) will be calculated wherever applicable. Adjustment of the α (type I error) level due to multiplicity is not applicable for this study as no planned formal statistical hypothesis testing will be performed.

Analysis and evaluation are defined separately for each parameter later in this document together with the description of rules for handling missing or incomplete data. The analyses will include vaccinated subjects with respect to the actual vaccine administered. For instance, if a subject is randomized to the Ad26.ZEBOV followed by MVA-BN-Filo vaccination schedule but is inadvertently vaccinated according to the MVA-BN-Filo followed by Ad26.ZEBOV vaccination schedule, the subject will be included in the latter vaccination schedule. Also, subjects who receive only the first (dose 1) vaccination will be included in the vaccination schedule with the corresponding dose 1 vaccine. On the other hand, subjects who will receive a homologous regimen (ie, Ad26.ZEBOV followed by another Ad26.ZEBOV or MVA-BN-Filo followed by another MVA-BN-Filo) will be excluded from summary analyses (ie, tables and graphs) and listed separately.

In general, the study data will be analyzed as follows:

- Categorical variables will be summarized with a frequency table presenting counts and percentages.

- Continuous variables will be summarized using the following statistics, as appropriate: number of observations, arithmetic mean, geometric mean, corresponding 95% confidence interval (CI), standard deviation, standard error, median, quartiles (Q1 and Q3), minimum and maximum.

Baseline value will be defined as the value of the last available assessment performed prior to dose 1 administration, unless specified otherwise.

For safety assessments, the *baseline value* will be an assessment performed prior to or on the date (only if time of assessment is missing) of the dose 1 administration. The baseline value for immunogenicity assessments will be an assessment performed before or on the date of dose 1 administration. In case of multiple values, the value closest to the vaccination will be used as the baseline.

Reference value (only for immunogenicity) will be defined as the assessment performed on the date of the dose 2 vaccination. In case of multiple values (on the same day of vaccination), the value closest to the vaccination will be used as the reference value.

Visit day will be determined relative to the actual day of vaccination (date of dose 1 administration or date of dose 2 administration).

Repeated assessments of immunogenicity and safety (including HIV viral load and CD4+ cell counts in HIV-infected subjects) will be allocated to analysis windows and periods based on [Table 2](#) and [Table 3](#), as described below.

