11.2. Analysis Sets

The Full Analysis set includes all subjects who were randomized and received at least 1 dose of study vaccine, regardless of the occurrence of protocol deviations. Safety data will be analyzed based on the Full Analysis set.

The Immunogenicity Analysis set includes all randomized and vaccinated subjects, who have data from baseline and at least 1 post-vaccination immunogenicity blood draw.

The Per Protocol Analysis set includes all randomized and vaccinated subjects, who received both the prime and boost vaccinations (administered not more than 10 days outside the visit window), have immunogenicity data from baseline and at least 1 post-vaccination evaluable immunogenicity sample, and have no major protocol violations influencing the immune response.

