The verbatim terms used in the CRF by investigators to report adverse events will be coded using the Medical Dictionary for Regulatory Activities (MedDRA). All reported adverse events (solicited local, solicited systemic, and unsolicited) will be included in the analysis. For each adverse event, the number and percentage of subjects who experience at least 1 occurrence of the given event will be summarized by group. Summaries, listings, datasets and/or subject narratives may be provided as appropriate, for those subjects who die, discontinue study vaccinations due to an adverse event, or experience a severe or serious adverse event. The analysis for solicited adverse events will be done on those subjects in the Full Analysis set for whom reactogenicity assessments are available in the database. The analysis of unsolicited adverse events will be done based on the Full Analysis set.

Physical Examination

Physical examination abnormalities will be listed. BMI will be calculated using the recording of height at screening.

Vital signs

Vital signs abnormalities will be tabulated by worst abnormality grade.

Clinical Laboratory Tests

Laboratory abnormalities will be determined in accordance with Toxicity Table for Use in Trials Enrolling Healthy Adults ([Attachment 2](#)). Laboratory abnormalities will be tabulated per treatment group by worst abnormality grade.

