2.3. Analysis Sets

Full Analysis Set

The full analysis set includes all subjects who were randomized and received at least 1 dose of study vaccine (Ad26.ZEBOV, MVA-BN-Filo or placebo), regardless of the occurrence of protocol deviations.

Immunogenicity Analysis Set

The immunogenicity analysis set includes all randomized and vaccinated subjects, who have at least 1 post-vaccination (ie, after the date of vaccination) evaluable immunogenicity sample.

Per Protocol Analysis Set

The per protocol analysis set includes all randomized and vaccinated subjects, who received both the dose 1 and dose 2 vaccinations (administered within the protocol-defined visit window), have at least 1 post-vaccination (ie, after the date of vaccination) evaluable immunogenicity sample, and have no major protocol violations influencing the immune responses.

The primary immunogenicity analysis will be performed on the per protocol analysis set. The analysis on the immunogenicity analysis set will be included as sensitivity analysis only if more than 10% of the subjects are excluded from the per protocol analysis set. For subjects who received dose 1 (ie, only first vaccination) but not dose 2 while continuing their planned visit schedule, the immune response measurements after the planned (ie, upper limit of the analysis visit window that covers the target day for the second vaccination) but not administered dose 2 will not be included in graphs and tables showing descriptive statistics. These measurements will however be shown in listings, together with the indication that they are not used in the analysis.

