7. SAFETY

The safety and tolerability data include the following:

- AEs (unsolicited AEs) collected from signing of the informed consent form (ICF) onwards until the 42-day Post-dose 2 visit.
- Serious adverse events (SAEs) and immediate reportable events (IREs) collected from signing of the ICF onwards until the end of the study.
- Solicited local and systemic AEs (reactogenicity) collected until 7 days after each administration of study vaccine.

The safety and tolerability data will be summarized based on the full analysis set. The analysis will be based on the actual dose (ie, dose 1 and dose 2 for the first and second vaccinations,

respectively) that the subjects received. For example, if dose 2 is not administered to a subject, then that subject will not be included in the analysis of AEs in the Post-dose 2 period. Focus will be on safety signals detected during the Post-dose 1 and Post-dose 2 periods, as well as the Regimen period (ie, combined Post-dose 1 and Post-dose 2 periods).

In general, safety data will be evaluated separately for each part of the study. Within each part, the data will primarily be presented by cohort (healthy and HIV-infected) and by vaccination schedule. Secondly, the data from Parts 1 and 2 of the study will be pooled (ie, 14-day interval regimen) and presented separately for the healthy and HIV-infected cohorts. See [Table 4](#) for a schematic overview the subgroups to be considered for the safety analysis.

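### The SAP drops subjects given the same vaccine twice from all tables without excepting safety, in conflict with its own full analysis set

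*SAP*

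**What the plan says.** SAP section 2 (General Analysis Definitions) sets an as-treated rule: "The analyses will include vaccinated subjects with respect to the actual vaccine administered". It then deals with three kinds of departure from the assigned regimen.

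- A subject given the other active schedule by mistake is counted under the schedule received.
- A subject given dose 1 only is counted under the schedule that starts with that vaccine.
- A subject given Ad26.ZEBOV twice or MVA-BN-Filo twice "will be excluded from summary analyses (ie, tables and graphs) and listed separately".

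SAP 2.3 defines the safety population differently: "The full analysis set includes all subjects who were randomized and received at least 1 dose of study vaccine", and this holds "regardless of the occurrence of protocol deviations". SAP section 7 says "The safety and tolerability data will be summarized based on the full analysis set", and Protocol 11.2 agrees: "Safety data will be analyzed based on the Full Analysis set". SAP section 5 uses the same set for subject information. Protocol 11.4 adds: "All reported adverse events (solicited local, solicited systemic, and unsolicited) will be included in the analysis".

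SAP section 3, which records changes to the planned analysis, redefines the immunogenicity and per protocol sets and drops an adherence analysis. It does not mention this exclusion.

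**The concern.** The exclusion stands among the general definitions and is limited neither to immunogenicity nor to any analysis set. Taken literally, it reaches the safety, disposition and demographics tables. Those tables would carry the full-analysis-set label but omit vaccinated subjects who belong to that set.

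Safety is a primary endpoint (Protocol 9.2.1), and Protocol 12.2 names administration errors among the safety events of interest. The rule would therefore take out of the summary rates subjects whom the protocol marks for attention. It would also remove their data between dose 1 and dose 2. Over that interval they cannot be distinguished from a dose-1-only recipient of the same vaccine, whom the same paragraph keeps.

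**Working it through.** **1. How can such a subject arise?** Table 1 in both documents lists MVA-BN-Filo then Ad26.ZEBOV, Ad26.ZEBOV then MVA-BN-Filo, and the placebo arms. There is no homologous active arm, so the sequence can come only from an administration error.

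**2. Which tables conflict?**

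| Output | Population named | Literal effect of the SAP section 2 rule |
|---|---|---|
| Disposition, demographics (SAP 5) | Full analysis set | Subject missing |
| Post-dose 1 safety by schedule (SAP 7) | Full analysis set | Subject missing, although the dose 1 data are valid |
| Post-dose 2 and Regimen-period safety by schedule (SAP 7) | Full analysis set | Subject missing; no column describes the sequence received |
| Safety tables pooled by vaccine (dose) (SAP 7.1.3, 7.3.3) | Full analysis set | Subject missing, although each dose has a natural place |

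Only the third row has a reason for exclusion that comes from the table itself.

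**3. What remains visible?** The rule provides a separate listing. SAP 7.1 puts all reported adverse events in the listings. SAP 7.1.3 lists serious, fatal, vaccination-stopping, Grade 3 and immediate reportable events, with narratives for all of these except Grade 3. SAP 5.1 lists assigned and actual regimen for each subject.

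**4. Size for one dropped subject.** Let x of n subjects in a cell have the event.

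- Dropped subject had the event: the rate falls by x/n − (x−1)/(n−1) = (n−x)/[n(n−1)]. This is largest at x = 1, where it equals 1/n.
- Dropped subject did not have it: the rate rises by x/(n−1) − x/n = x/[n(n−1)]. At x = 1 and n = 20 this is 1/380, about 0.3 points.

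With the planned active cells of 20, 40 and 160, the worst case (the only event falls in the dropped subject) with exact 95% intervals is:

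| Cell | Kept | Dropped | Shift |
|---|---|---|---|
| 20 | 1/20 = 5.0% (0.13 to 24.9) | 0/19 (0 to 17.6) | 5.0 points |
| 40 | 1/40 = 2.5% (0.06 to 13.2) | 0/39 (0 to 9.0) | 2.5 points |
| 160 | 1/160 = 0.6% (0.02 to 3.4) | 0/159 (0 to 2.3) | 0.6 points |

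**5. Effect on precision.** Protocol 11.1 gives one-sided 97.5% upper limits when no event is seen. The formula 1 − 0.025^(1/N) reproduces them: 16.84% at N = 20 (stated 16.8%), 8.81% at N = 40 (8.8%), 2.28% at N = 160 (2.3%) and 0.80% at N = 460 (0.8%). The documents give no count of homologous recipients, so I assume a range of 1 to 5, all in the cell concerned. The limits become 17.6% to 21.8% at N = 20, 9.0% to 10.0% at N = 40, 2.29% to 2.35% at N = 160, and at most 0.81% at N = 460.

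**The case against.** The strongest reply has four parts.

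- **The safety section may govern.** The paragraph with the exclusion says that analyses are defined parameter by parameter later in the SAP. Section 7 then names the full analysis set, works from the doses actually received and does not repeat the exclusion. That reading is possible. The SAP does not say which text prevails, however, so two programmers could produce different denominators.
- **The rule has a rationale.** Tables are laid out by schedule received, and a homologous recipient received neither schedule. This stands for immunogenicity summaries by schedule and for Post-dose 2 and Regimen-period safety columns by schedule. It does not justify removal from disposition, demographics, Post-dose 1 tables or by-vaccine tables.
- **Nothing is hidden.** A reader might infer that serious events would disappear from the report. The documents do not support that, because listings and most narratives keep them. What is lost is their contribution to the rates.
- **No bias is shown.** A reader might also infer that the rule favours the vaccine. It is triggered by the product given at dose 2, not by outcome, and it is written in advance of the final analysis. The trial is descriptive with no formal hypothesis test, so no decision rule is affected.

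**Conclusion.** The conflict is real: SAP section 2 removes these subjects from every table and graph without excepting safety, while SAP 2.3, 5 and 7 and Protocol 11.2 and 11.4 require their inclusion. Which text governs safety is unresolved, and the departure is not declared in SAP section 3.

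The likely effect is small. Any single dropped subject with an event moves a rate by at most 1/n: 5.0, 2.5 or 0.6 points in cells of 20, 40 or 160. The 5.0-point figure needs a homologous recipient in the smallest active cell who is the only subject there with the event. Neither document reports that any such subject exists. At 460 subjects the effect on the zero-event limit is negligible.

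A reader might conclude that the exclusion should apply to per protocol immunogenicity alone. That goes too far. It would leave these subjects in immunogenicity-set and Post-dose 2 by-schedule summaries under a schedule they did not receive.

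**What to change.** Amend the sentence in SAP section 2 as follows.

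- Limit the exclusion to immunogenicity summaries by vaccination schedule, and to safety columns by schedule for the Post-dose 2 and Regimen periods.
- Keep these subjects in full-analysis-set disposition and demographics.
- Keep them in Post-dose 1 safety tables under the dose 1 vaccine received.
- Keep them in the planned tables pooled by vaccine (dose), according to the vaccine actually given at each dose.
- Footnote their serious, immediate reportable, fatal and Grade 3 events in the by-schedule tables.
- Record the remaining exclusion in SAP section 3.

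The cost is a short SAP revision, a programming flag and the footnotes. No new data and no new table type are needed, because SAP section 7 already works from doses received and the by-vaccine tables are already planned. If the listing of assigned and actual regimens shows no homologous recipient, the change affects no result but still removes the contradiction.

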2.1. Analysis Visit Windows and Periods

Because subjects do not always adhere to the protocol visit schedule, the following rules will be applied to assign actual visits (immunogenicity and safety [ie, including only HIV viral load and CD4+ cell counts in HIV-infected subjects]) to analysis visits. The analysis visit windows and target days for each visit are displayed in [Table 2](#). The reference day will be defined as:

- Day of first (dose 1) vaccination if the actual visit occurs prior to the second (dose 2) vaccination.
- Day of second vaccination (dose 2) if the actual visit occurs after the second vaccination.

Only the analysis time points and assays that are in scope for final statistical analysis are to be considered when assigning assessments to analysis visit windows. If a subject has 2 or more assessments within the same interval (analysis visit window), the one closest to the target day will be used for generating tables with descriptive statistics and graphical displays presenting data per time point. If 2 assessments are equidistance from the target day within the same interval, the latest assessment will be used. All assignments will be made in chronological order.

Because the analysis of adverse events (AEs), vital signs and laboratory abnormalities (except HIV viral load and CD4+ cell counts in HIV-infected subjects) will be presented per period (and not per time point), these will be assigned to the analysis period and/or phase based on [Table 3](#).

For HIV viral loads and CD4+ cell counts in HIV-infected subjects, the electronic case report form (eCRF) visit schedules will be used for the post baseline assessments. If only unscheduled visits are present for a time point, then the one closest to the scheduled visit will be used. If distances of multiple assessments to the scheduled visit are equal, the measurement with the latest date will be used.

Table 2: Analysis Visit Windows

Time Interval (Label on Output)	Time Interval PP ^a (Day)	Time Interval IG ^b (Day)	Target Time Point (Day)
Prior to dose 2 vaccination			
Day 1 (Baseline)	≤ 1	≤ 1	1
Day 15 (14 days Post-dose 1)	[12; 18]	[2; 21]	15
Day 29 (28 days Post-dose 1)	[26; 32]	≥ 22	29
After dose 2 vaccination			
Day 36 (21 days Post-dose 2)	[19; 25]	[2; 32]	22
Day 50 (21 days Post-dose 2)			
Day 57 (42 days Post-dose 2)	[40; 46]	[33; 112]	43
Day 71 (42 days Post-dose 2)			
Day 195 (180 days Post-dose 2)	[166; 196]	[113; 273]	181
Day 209 (180 days Post-dose 2)			
Day 380 (365 days Post-dose 2)	[336; 396]	≥ 274	366
Day 394 (365 days Post-dose 2)			

^a The analysis based on the per protocol (PP) analysis set will be restricted to data points that fall within this window (ie, protocol-defined window).

^b The analysis based on the immunogenicity analysis set will be restricted to data points that fall within this window.

Note 1: The analysis windows and target days are based on the relative day (ie, with respect to reference day [day of dose 1 or dose 2 administration]).

Note 2: Day of dose 2 is also considered as Day 1 with respect to the second vaccination (ie, for calculating target days that fall after the second vaccination).

Note 3: Day 36, Day 57, Day 195 and Day 380 apply only to the 14-day interval vaccination schedule. While Day 50, Day 71, Day 209 and Day 394 apply only to the 28-day interval vaccination schedule.

Table 3: Analysis Periods

Phase	Period	Interval	
		From	To
Screening		00:00 on the date of signing the informed consent form	One minute prior to dose 1 administration on Day 1
Regimen*	Post-dose 1	Date and time of dose 1 administration	Minimum of: 
 a) 23:59 on the date of last contact (for early study discontinuation) b) 23:59 on the date of relative Day 29 Post-dose 1 c) 23:59 on planned visit day of dose 2 administration (in case dose 2 is not administered) d) one minute prior to dose 2 administration [□] e) 23:59 on the date of database cut-off (in case of interim analysis)
Post-dose 1 FU		One minute after the end of the Post-dose 1 period	Minimum of: 
 a) 23:59 on the date of last contact (for early study discontinuation or completion) b) one minute prior to dose 2 administration c) 23:59 on the date of database cut-off (in case of interim analysis)
Regimen*	Post-dose 2	Date and time of dose 2 administration	Minimum of: 
 a) 23:59 on the date of last contact (for early study discontinuation or completion) b) 23:59 on the date of relative Day 29 Post-dose 2 c) 23:59 on the date of database cut-off (in case of interim analysis) 
Note: subjects who do not receive dose 2 will not have a Post-dose 2 period.

Post-dose 2 FU		One minute after the end of the Post-dose 2 period	Minimum of: 
 a) 23:59 on the date of database cut-off (in case of interim analysis) b) 23:59 on the date of last contact (for early study discontinuation or completion)

[□] For dose 2 administered earlier than Day 29 Post-dose 1 visit.

Note 1: * Regimen period includes both the Post-dose 1 and Post-dose 2 periods.

Note 2: FU = follow-up.

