9.2. Endpoints

9.2.1. Primary Endpoints

The primary endpoints are:

- Safety as determined by:
 - Adverse events, collected until the 42-day post-boost visit.
 - Serious adverse events and IREs, collected until the end of the study.
 - Solicited local and systemic adverse events (reactogenicity), collected until 7 days after each vaccination.

- Magnitude of humoral immune response against the EBOV GP by determining binding antibody levels using ELISA (in ELISA units/mL and/or endpoint-titers) until the 21-day post-boost visit.

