7.1. Adverse Events

The analysis of AEs is based on the medical dictionary for regulatory activities (MedDRA) coded terms as provided in the clinical database. All reported AEs (solicited local, solicited systemic, and unsolicited) during the vaccination periods (Post-dose 1 and Post-dose 2) (ie, AEs following vaccination and AEs that have worsened since baseline) will be included in the analysis. Listings of AEs will include all reported AEs.

Note that the AEs include any occurrence that is new in onset or aggravated in severity, toxicity grade or frequency from the baseline condition, or clinically relevant abnormal results of diagnostic procedures, including clinically relevant laboratory test abnormalities.

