7.1.3. Analysis Methods

In general, the AEs following vaccination will be summarized (ie, tables of descriptive statistics) by vaccination schedule and presented per period/phase. Similar summary tables will also be provided pooled by vaccine (dose).

Furthermore, unsolicited AEs will be summarized (showing number and percentage) by System Organ Class (SOC) and Preferred Term (PT). Solicited AEs (recorded by day) will be converted into the analysis format of unsolicited AEs (recorded by event), as detailed in Attachment 2. These solicited AEs will be summarized by class (local, systemic) and Preferred Term. For

solicited as well as unsolicited AEs, tables focusing on severity will be created. Focus will also be on the relationship (to the study vaccine) of the solicited systemic and unsolicited AEs.

The SAEs, AEs with fatal outcome, AEs leading to permanent stop of study vaccination, Grade 3 AEs and IREs will also be listed. A table summarizing all those parameters will further be created and presented per analysis period and vaccination schedule. Summary tabulations by SOC and PT for each of the category of events (ie, SAEs, AEs with fatal outcome, AEs leading to permanent stop of study vaccination, Grade 3 AEs and immediate reportable events) will also be generated on the entire reporting period. Subject narratives will be generated for these events, except Grade 3 AEs.

For the most frequent (at least 10% of subjects in any vaccination schedule) solicited local and systemic AEs, the duration and time to first onset of the events will also be summarized. If a subject experiences more than 1 occurrence of a solicited event, the maximum duration of the events will be used. The time to first onset is defined as:

$$[\textit{date of first onset} - \textit{reference date} + 1]$$

The reference date is the start date of each vaccination period (ie, Post-dose 1 or Post-dose 2). Duration and time to onset of AEs will be expressed in days.

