As the AE starts after the Screening Phase and after the start of the Post-dose 1 period, it is only assigned to the Post-dose 1 period.

Remarks:

- In addition to the date information, time information is considered to allocate AEs to periods, if available.

- The imputation of missing end dates of ongoing AEs will only be used to derive the duration of the event (ie, to give an indication of the minimum duration). The imputed end dates will not be shown in the data listings.

Step 2: Combination of events:

Overlapping/consecutive events are defined as events of the same subject with the same preferred term which have at least 1 day overlap or for which the start date of an event is 1 day after the end date of the preceding event. Overlapping/consecutive events may be combined into one AE or not, according to the following rules:

- 1) If overlapping/consecutive events start in a non-active phase (Screening or any of Post-dose FU phases) followed by an AE in an active (Post-dose 1 or Post-dose 2) period, they are allocated to their respective periods/phases and are considered as separate events.
 - 2) In case overlapping/consecutive events start within a single period/phase, they are considered as one and the same AE. The individual events which contribute to this AE are retained as individual records in the Analysis Data Model (ADaM) database but are assigned the same onset, period/phase, and total duration.
 - 3) In case overlapping/consecutive events start in an active period followed by a non-active phase, they are allocated only to the active period and are considered as one and the same AE. The individual events which contribute to this AE are retained as individual records in the ADaM database but are assigned the same onset, period, and total duration.
 - 4) In case an active period is followed by another active period, and the overlapping/consecutive events start in both periods, they are allocated to their respective period and are considered as separate AEs. The same rule applies for 2 non-active phases.
- Remarks:
 1. Time is not considered when determining overlap of events.
 2. Events can only be combined into one and the same AE if their start and stop dates are known.
 3. In case the completely missing end date is imputed (for calculation of duration), this date is also considered as a complete date.

Examples:

Screening phase: start date: 14JUN2016 - stop date: 28JUN2016

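### No planned table gives unsolicited-AE incidence over the primary endpoint window: the Regimen period ends 28 days after dose 2, the endpoint at the 42-day visit

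*SAP*

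**What the plan says.** Protocol 9.2.1 lists as the first component of the primary safety endpoint "Adverse events, collected until the 42-day post-boost visit". Protocol 11.4 repeats that window and adds: "All reported adverse events (solicited local, solicited systemic, and unsolicited) will be included in the analysis". SAP Section 7 gives the same 42-day collection window for unsolicited AEs.

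The SAP's analysis periods are shorter. Table 3 in SAP 2.1 ends Post-dose 1 no later than "23:59 on the date of relative Day 29 Post-dose 1" and Post-dose 2 no later than "23:59 on the date of relative Day 29 Post-dose 2". Note 1 to that table builds the Regimen period from these two periods only. Later time goes to the Post-dose 1 FU and Post-dose 2 FU phases.

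On what is tabulated, two SAP sections differ:

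- SAP 7.1 defines the AE analysis as "All reported AEs (solicited local, solicited systemic, and unsolicited) during the vaccination periods (Post-dose 1 and Post-dose 2"), and promises the complete set of AEs only in listings.
- SAP 7.1.3 says that "the AEs following vaccination will be summarized (ie, tables of descriptive statistics) by vaccination schedule and presented per period/phase", which could be read to include the FU phases.

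SAP 7.1.3 also plans summaries by SOC and PT that are not tied to a period, but only for SAEs, fatal AEs, AEs leading to permanent stop of vaccination, "Grade 3 AEs and immediate reportable events) will also be generated on the entire reporting period".

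**The concern.** The study is descriptive and tests no formal hypothesis, so the incidence estimate is itself the primary safety result. If the main all-grade unsolicited-AE table is the Regimen-period table, the reader receives incidence to 28 days after dose 2 where the protocol names 42 days. Nothing in SAP Section 3 marks this as a departure.

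The events at stake are limited. Solicited AEs are fully covered, and the severe and serious categories have tables over the entire reporting period. What is left is non-serious, non-IRE, Grade 1 or 2 unsolicited AEs that did not stop vaccination, with onset on relative Days 30 to 43 after dose 2 or in Post-dose 1 FU. An FU event that overlaps or directly follows an active-period event of the same preferred term is not lost: under SAP Attachment 1, Step 2, rule 3, "they are allocated only to the active period and are considered as one and the same AE".

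**Working it through.** **1. Day count.** SAP Table 2 takes the day of dose 2 as Day 1, so relative day = days since dose 2 + 1. For 21, 42, 180 and 365 days this gives 22, 43, 181 and 366, the four target days in Table 2. Study days also agree with Protocol Table 2: 15 + 42 = 57 and 29 + 42 = 71. Relative Day 29 is therefore 28 days after dose 2, and the 42-day visit is relative Day 43, window 40 to 46.

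**2. Days after dose 2 outside the Regimen period.** 43 − 29 = 14. Over the visit window: 40 − 29 = 11 to 46 − 29 = 17.

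**3. Days before dose 2 outside the Regimen period.** Post-dose 1 also stops at Day 29.

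- 28-day schedule (400 of 575 planned subjects), boost inside its window: the latest day is 29 + 3 = 32, and 32 − 29 = 3 days, the last partial.
- 28-day schedule, boost postponed under Protocol 6.2: the latest day is 29 + 3 + 10 = 42, and 42 − 29 = 13 days, the last partial.
- 14-day schedule: the latest postponed boost is 15 + 3 + 10 = 28, so there is no gap.
- A subject without dose 2 leaves Post-dose 1 at the planned dose 2 visit day or Day 29, whichever comes first. Later AEs fall in Post-dose 1 FU.

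**4. Can the planned tables be combined to give the endpoint?** If the FU phases are not tabulated (SAP 7.1), no. If they are (SAP 7.1.3), still no: a subject with events in several periods is counted in each, so subject percentages cannot be added.

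**5. Illustrative size.** The documents give no unsolicited-AE incidence or timing for this study, so the inputs are assumptions: Regimen-period incidence p; AE rate on Days 30 to 43 equal to r times the Regimen-period average; one constant rate shared by all subjects; no merging of events. With L the Regimen length in days (28 + 28 = 56, or 14 + 28 = 42):

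endpoint-window incidence = 1 − (1 − p)^(1 + r × 14/L)

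| Schedule | p | r = 0.25 | r = 0.5 | r = 1 |
|---|---|---|---|---|
| 28-day, L = 56 | 20% | 21.1% | 22.2% | 24.3% |
| | 40% | 41.9% | 43.7% | 47.2% |
| | 60% | 62.2% | 64.3% | 68.2% |
| 14-day, L = 42 | 20% | 21.5% | 22.9% | 25.7% |
| | 40% | 42.5% | 44.9% | 49.4% |
| | 60% | 62.9% | 65.7% | 70.5% |

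Example: p = 0.40, L = 56, r = 1 gives 1 − 0.60^1.25 = 0.472.

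**The case against.** The strongest reply is that the FU phases are probably tabulated already. SAP 7.1.3 speaks of periods and phases, Attachment 1 allocates AEs to FU phases in detail, and SAP Section 7 describes the post-dose periods as a focus, not as a limit. Table shells are not among the documents, so this reading cannot be excluded. It would put the Day 30 to 43 events in a Post-dose 2 FU column. It conflicts with the wording of SAP 7.1, however, and still supplies no subject-level incidence over the endpoint window.

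Three further points carry some weight:

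- Post-dose 2 FU runs to last contact and so mixes AEs collected to Day 43 with SAEs and IREs collected to study end. This is a lesser difficulty, because after the 42-day visit only SAEs and IREs are collected and these have their own summaries. The non-additive percentages carry the argument.
- Table 3 states its cut-off openly. What is missing is an entry in Section 3, not the definition of the period. It can also be argued that the protocol's 42 days describe collection and leave the tabulation to the SAP. Yet Protocol 9.2.1 names that window as the endpoint, and 11.4 includes every reported AE.
- The illustration rests on assumed rates. If some subjects are more prone to AEs than others, fewer first events occur late and the upper figures are too high. The pre-boost gap touches only subjects boosted after Day 29, not all 400.

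**Conclusion.** The concern holds. Followed as written, the SAP gives no all-grade unsolicited-AE incidence over the primary endpoint window, and it does not declare the shorter window as a change. That 14 of the 42 days after dose 2 are outside the Regimen period follows directly from the documents. The effect on incidence is not known: under the stated assumptions it is about 1 to 3 percentage points if AEs cluster early (r = 0.25), and up to about 10 points if the rate does not fall.

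The cut is the same for active and placebo within a schedule, so the fault is an incomplete and undeclared summary of a primary endpoint, not a biased comparison. It should be fixed.

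**What to change.** - Add one table of all unsolicited AEs from dose 1 to the 42-day Post-dose 2 visit, including Post-dose 1 FU, each subject counted once, and name it the primary unsolicited-AE summary. State where the window ends for subjects without dose 2.
- Keep the Day 29 periods as supplementary summaries.
- Reconcile SAP 7.1 with 7.1.3 on whether the FU phases are tabulated.
- If the 28-day window is meant to be the main analysis, declare it in SAP Section 3 as a change from Protocol 9.2.1 and 11.4.

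The cost is one table run and some SAP wording. The data are already collected. Table 3 can stay as it is, so the laboratory, vital-sign and concomitant-therapy periods are not affected.
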